1. Clinicians randomized to the overdose notification group will exhibit a greater reduction in weekly MME from the pre- to post-period compared to clinicians randomized to the control group for fatal and non-fatal overdoses.
2. Among the clinicians who prescribed at least one opioid in the study period, those randomized to the overdose notification group will exhibit a greater reduction in the proportion of a clinician's patients prescribed at least 50 daily MME from the pre- to post-period compared to clinicians randomized to the control group for fatal and non-fatal overdoses.

b) Number of subjects:

AltaMed Health Services is a private health system in Los Angeles, California. AltaMed has 35 clinics with 134 clinicians with 17,674 such patients. Clinicians meeting inclusion criteria will be enrolled in the study. Northwestern Medicine is a regional health system affiliated with an academic medical center located in the Chicago region of Illinois and includes 60 primary care clinics that contain 387 clinicians with 12,552 patients using chronic opioid therapy for noncancer pain—on opioids for greater than three months.

c) Mechanism for subject selection or exclusion:

Eligible physicians and patients will be identified using outpatient opioid prescribing data

from electronic medical records. A clinician is eligible for inclusion if: 1) s/he prescribed a qualifying scheduled drug to a patient in the 12 months prior to their fatal or non-fatal overdose 2) the patient is 18 years old or older at the time of the overdose, 3) s/he practices within a health system enrolled in the study, and 4) the overdose occurs during the 12-month observation period.

A patient is eligible for identification in a physician notification if s/he (a) has been prescribed an opioid by an eligible clinician (b) has a documented overdose event in EHR or mortality data. Patients without overdose events will be excluded. Patients with fatal overdoses in Los Angeles County will be excluded to avoid redundancy with existing notification practices.

[figure not shown]
d) Duration of intervention:

The duration of the overdose notification intervention is one day.

e) Total duration which study will be performed (data collection, intervention, and analysis period):

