discontinuation of opioids for persons whose most recent prescription exceeds 49 MME daily dose; or as reported to study staff (10).

If there is a significant difference in the prevalence of these adverse events or overdoses between the treatment and control groups, the differences will be reported to the Data and Safety Monitoring Board and in the publication of the study results. *It is important to note that prior quality evaluations of these letters observed no additional risk of abrupt changes to opioid prescribing upon receipt of a letter (<https://pubmed.ncbi.nlm.nih.gov/30093595/>).*

- Management of overdose and prescribing data poses no more than minimal privacy risks. USC, health systems and IDPH comply with all local and federal security regulations protecting privacy. Identified patient data will be destroyed after the notifications have been prepared. A HIPAA Limited Data Set that includes outpatient prescribing records, overdose events, and notification status will be transferred to USC for data analysis in USC's HIPAA compliant enclave.

b) Experimental Procedures:

Randomization and Allocation. Overdose clusters are the units of randomization in this study. A cluster consists of all clinicians who prescribed one or more of the included scheduled drugs to the patient in the year prior to the overdose. Overdose clusters will be randomized to the overdose notification group or the control group, stratified by the health system which defines the cluster in the year prior to the overdose event.

Allocation will be concealed until after the study groups are assigned. Clinicians who practice at multiple clinics will be assigned to the clinic at which the majority of their visits occurred in the year prior to the overdose event. If clinicians belong to more than one cluster (have multiple patients with opioid-related overdoses), they will be randomly assigned to one of those patients and placed in the corresponding study group. If clinicians belonging to more than one cluster are randomized to the intervention group, they will only receive an overdose notification regarding the one patient to whom they were randomly assigned.

Intervention. Clinicians in the intervention group receive a letter notifying them of their patient's fatal or non-fatal overdose. As described above, we will identify overdoses from electronic health record data from emergency departments and state vital records.

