If randomized to the overdose notification group, physicians who prescribed a qualifying prescription to the deceased or surviving patient in the year prior to their overdose will be informed of the overdose via letter. The letters will alert prescribers to the patient's opioid-related overdose, recommend the use of their state's PDMP, and list evidence-based interventions to lower opioid-related overdoses (Appendix 2 and 3).

Controls. Clinicians in the control group will receive guideline education in the form of the CDC pocket guide and no notification of a patient overdose event (See Appendix 5). https://www.cdc.gov/drugoverdose/pdf/TurnTheTide_PocketGuide-a.pdf

D. Statistical Analysis Plan

Patients who experienced an opioid overdose will be randomized to either the letter intervention or control. We will analyze how the prescribing behavior of those patients' clinicians changed pre-to-post intervention. We will use means and medians for continuous measures for sample descriptive statistics, frequencies for count data and standard deviations, and interquartile ranges for variance. We will evaluate changes in opioid prescribing rates by group using an intent-to-treat difference-in-differences regression model on clinician hydrocodone morphine equivalent weekly dose. The coefficient for the group assignment, overdose type, and time interaction, also known as the difference-in-differences estimator, denotes the change over time in 5 MME hydrocodone pills for prescribers in the intervention group compared to prescribers in the control group for both fatal and nonfatal overdose victims. The use of a mixed-effects hierarchical knotted spline Poisson regression model offers a flexible way to accommodate non-linear trends in prescribing by group before and after introducing the intervention. This model places a knot at the intervention start date allowing slopes before and after the introduction of the intervention to vary for each group. Our primary outcome is the daily average number of 5 MME hydrocodone pills. If we have an excess of data clustering at zero, indicating weeks during which a physician wrote no opioid prescriptions, we will use a zero-inflated or left-censored regression. The regression model estimating the association between letter assignment and weekly 5 MME hydrocodone pills prescribed is shown in Eq. 1:

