$$(pills)_{ijk}^* = \beta_1 + \beta_2 Time_{ij} + \beta_3 (Time_{ij} - t^*) + \beta_4 Group_i + \beta_5 Overdose Type_k + \beta_6 Group_i * Overdose Type_k + \beta_7 Time_{ij} * Group_i + \beta_8 (Time_{ij} - t^*) * Group_i + \beta_9 Time_{ij} * Overdose Type_k + \beta_{10} (Time_{ij} - t^*) * Overdose Type_k + \beta_{11} Time_{ij} * Group_i * Overdose Type_k + \beta_{12} (Time_{ij} - t^*) * Group_i * Overdose Type_k + \eta + \delta_{i(k)} + error$$

where $(pills)_{ijk}^*$ denotes the dependent variable for clinician i in week j , $Time_{ij}$ is the study week indexed by j , t^* is the spline knot for the start of the intervention, $(Time_{ij} - t^*)$ is a truncated line function that is equal to $(Time_{ij} - t^*)$ when $Time_{ij} > t^*$ and 0 otherwise to allow for nonlinear trends in prescribing following the intervention, $Group_i$ is dichotomous for the overdose notification intervention group, $Overdose Type_k$ is dichotomous for a fatal overdose, η is the clinic random effect, and $\delta_{i(k)}$ is the random effect for each clinician i who prescribed to patient k who suffered an overdose.

The mixed logistic regression model for our secondary outcomes is shown in Eq. 2:

$$(high dose Rx)_{ijk} = \beta_1 + \beta_2 Time_{ij} + \beta_3 Group_i + \beta_4 Overdose Type_k + \beta_5 Group_i * Overdose Type_k + \beta_6 Time_{ij} * Group_i + \beta_7 Time_{ij} * Overdose Type_k + \beta_8 Time_{ij} * Group_i * Overdose Type_k + \eta + \delta_{i(k)} + error$$

where $(high\ dose\ Rx)_{ijk}$ is whether the visit had a high dose prescription of 50 MME or greater (yes vs. no) for clinician i , $Time_{ij}$ is the study period (pre- vs. post-intervention) indexed by j , $Group_i$ is dichotomous for the overdose notification intervention group, $Overdose\ Type_k$ is dichotomous for a fatal overdose, η is the clinic random effect, and $\delta_{i(k)}$ is the random effect for each clinician i who prescribed to patient k who suffered an overdose. We will compute the estimated pre- to post-intervention change in the mean proportion of high dose patient visits for each of the four intervention groups: nonfatal control, nonfatal letter, fatal control, fatal letter. The proportion will be calculated by dividing the total number of patient visits where an opioid of at least 50 MME was prescribed by the total number of opioid prescriptions.

E. Privacy of Individuals and Confidentiality of Data

We will utilize two types of data for this study:

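### Randomisation is stratified by health system but not by overdose type, which defines the named estimator; if fatal clusters are few, precision of the fatal contrast is left to chance

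*Combined protocol and SAP*

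**What the plan says.** Section C.b (Randomization and Allocation) states: "Overdose clusters are the units of randomization in this study". Each cluster goes to the letter arm or to the control arm, and the allocation is "stratified by the health system which defines the cluster in the year prior to the overdose event". No second stratification factor is named, and the section gives no allocation ratio, block size or other restriction.

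Section D identifies its estimator as follows: "The coefficient for the group assignment, overdose type, and time interaction, also known as the difference-in-differences estimator". Overdose type in Eq. 1 and Eq. 2 "is dichotomous for a fatal overdose". The three-way terms are β11 and β12 in Eq. 1 and β8 in Eq. 2. For the high-dose outcome, section D also asks for the pre-to-post change "for each of the four intervention groups: nonfatal control, nonfatal letter, fatal control, fatal letter".

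Section B.c removes fatal events from one of the two systems: "Patients with fatal overdoses in Los Angeles County will be excluded to avoid redundancy with existing notification practices". The synopsis says that both letter types go out in Chicago. All fatal clusters therefore belong to the Northwestern stratum.

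Section B.f describes separate sources at Northwestern. Non-fatal events come from a single extract at the start, and fatal events from quarterly exchanges with the state health department. It does not say whether the quarterly lists are randomised separately.

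**The concern.** A cluster exists only because an overdose has been identified, so its type is known before allocation and could serve as a stratum. Stratifying by health system can balance the Northwestern clusters as a whole, but it does not control how the fatal ones among them divide between arms.

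The precision of the fatal letter-versus-control contrast depends mainly on the smaller of the two fatal cells, and the three-way interaction inherits that imprecision. A lopsided split widens the interval for the coefficient that section D names. If one fatal cell were empty, the coefficient could not be estimated.

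**Working it through.** **Inputs.** From the documents: health system is the only stratum (C.b), there are no Los Angeles fatal clusters (B.c), and the estimator includes overdose type (D). The documents give no number of fatal clusters, no allocation method, no sample size and no power, so there is no figure of the plan's own to reproduce. Assumed: n = 6 to 20 fatal clusters, with 30 and 40 for comparison; simple 1:1 allocation; clusters of equal information.

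**Formulas.** With k of n fatal clusters in the letter arm, k follows Binomial(n, 0.5).
- A 75:25 or worse split means min(k, n−k)/n ≤ 0.25.
- Variance inflation against an equal split is (1/k + 1/(n−k)) / (4/n).
- The mean inflation is taken over splits with both arms non-empty.

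Example, 8:2 with n = 10: (1/8 + 1/2)/(4/10) = 0.625/0.4 = 1.56.

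Example of the mean, n = 6: the 5:1, 4:2 and 3:3 splits have 12, 30 and 20 of the 64 outcomes and inflations 1.8, 1.125 and 1. The mean is (12×1.8 + 30×1.125 + 20×1)/62 = 75.35/62 = 1.215.

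| n | 75:25 or worse | All in one arm | Mean inflation |
|---|---|---|---|
| 6 | 14/64 = 21.9% | 2/64 = 3.1% | 1.215 |
| 8 | 74/256 = 28.9% | 2/256 = 0.8% | 1.184 |
| 10 | 112/1,024 = 10.9% | 2/1,024 = 0.2% | 1.146 |
| 12 | 598/4,096 = 14.6% | 0.05% | 1.116 |
| 16 | 5,034/65,536 = 7.7% | under 0.01% | 1.079 |
| 20 | 43,400/1,048,576 = 4.1% | under 0.01% | 1.060 |
| 30 | 0.5% | under 0.01% | 1.037 |
| 40 | 0.2% | under 0.01% | 1.027 |

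The second column jumps because counts are whole numbers. Some sizes between the rows fall lower: n = 19 gives 10,072/524,288 = 1.9%. The mean inflation is the steadier guide.

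**Would balance across Northwestern as a whole suffice?** Suppose arm totals there are fixed and equal over an assumed 100 clusters (hypergeometric). With 10 fatal clusters the chance of 75:25 or worse is 9.2%, against 10.9% under simple allocation, and the mean inflation is 1.129. With 20 fatal clusters the figures are 2.3% and 1.047. With an assumed 40 clusters in total, they are 6.5% and 1.104 for 10 fatal clusters, and 0.4% and 1.028 for 20. Overall balance helps little unless fatal clusters make up a large share of the stratum.

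**After the change.** With permuted blocks inside a fatal stratum, the arms can differ by at most half a block. With blocks of 4 and n = 10, the worst split is 6:4, and the inflation is (1/6 + 1/4)/(4/10) = 1.04.

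**The case against.** The strongest reply is that nothing shows fatal clusters to be few. Section B.b gives 387 clinicians and 12,552 patients at Northwestern, but no overdose or death rate. A reader might infer scarcity from the nature of the event, but the documents do not support it as a fact, and 6 to 20 is a range in which the problem is visible. This stands, and the point is conditional for that reason.

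The allocation method is also unstated. If the quarterly fatal lists are block-randomised on their own, the fatal arms are already close to balanced. This stands too.

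The average loss is modest. Inflation of 1.060 to 1.215 widens the fatal interval by √1.060 − 1 = 3% to √1.215 − 1 = 10%. The proportional effect on the three-way coefficient is smaller, because that also carries the variance of the non-fatal contrast. If fatal clusters are few, most of the imprecision comes from their number, which stratifying cannot cure.

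A reader might also infer bias. The documents do not support that: allocation is random, and both equations contain overdose type with its group and time interactions. Nor are the four arm-by-type cells a general reporting rule. Section D asks for them for the high-dose outcome only. Hypothesis 1 can be read as an overall letter-versus-control comparison, so how central the fatal contrast is remains open.

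Two things survive. The factor in the named estimator is not protected by the design. And health system, the factor that is stratified, has no term in Eq. 1 or Eq. 2; the clinic random effect absorbs system differences only in part.

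**Conclusion.** The gap holds in conditional form. Under simple 1:1 allocation with an assumed 6 to 20 fatal clusters, a 75:25 or worse split has a chance of about 4% to 29% at the tabulated sizes, and the variance of the fatal contrast rises on average by 22% to 6%. From about 30 clusters the risk is small: 0.5% for such a split and under 4% average inflation. An empty fatal cell is a realistic worry only with very few clusters (3.1% at 6, 0.2% at 10).

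The result rests on the assumed cluster count, simple allocation and equally informative clusters. No effect on the trial's power can be given, since the documents state no power or sample size calculation. The consequence is lost precision, not a biased estimate.

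**What to change.** 1. State in section C.b the expected or actual number of fatal clusters, the allocation ratio and method, and whether the quarterly fatal lists are randomised separately.
2. For clusters not yet allocated, randomise in permuted blocks within three strata: AltaMed non-fatal, Northwestern non-fatal and Northwestern fatal. Blocking is essential, because simple randomisation inside the strata would change nothing. The blocks balance clusters and only approximately balance clinicians, since cluster sizes vary and a clinician in several clusters is assigned at random to one patient.
3. Whether or not allocation is finished, add a health-system term to Eq. 1 and Eq. 2. They already contain overdose type, so the analysis would then reflect the randomisation strata. This does not repair a split that has already come out lopsided.
4. Report fatal clusters and clinicians per arm.

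The cost is a small change to the allocation program, one model term and one line in a results table. Three strata carry little risk of over-stratification.

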Application of Economics & Social psychology to improve Opioid Prescribing Safety (AESOPS) Trial 2 is a multi-site randomized trial that takes place among a clinic organization in Los Angeles, California (AltaMed Health Services) and one in Chicago, Illinois (Northwestern University). Participants in the trial are clinicians. Observations are visits where opioids are prescribed. Clinicians are randomized to receive either: 1) guidelines on opioid prescribing, or 2) information on an opioid harm experienced by one of their patients (non-fatal or fatal overdose). In Los Angeles, fatal overdose letters are already required by the County, therefore, only non-fatal overdose letters will be sent to clinicians in Los Angeles. These will be signed by the County Public Health Officer. In Chicago, Illinois, both types of letters will be sent. Outcomes are milligram morphine equivalents ordered by each participating clinician per week. A secondary outcome is referrals to medication assisted treatment. These data are collected from the electronic health record systems at AltaMed and Northwestern Medical Center. Determining overdoses involves connecting data on overdoses between hospital systems, or in the case of Illinois, state vital records. More specifically, non-fatal overdoses in Los Angeles connect opioid prescribing at AltaMed with Los Angeles County emergency department data (See Appendix 1, Figure 1a), non-fatal overdoses at Chicago's Northwestern University involve a search of the internal database that connects that University's outpatient clinic data with emergency department data (See Appendix 1, Figure 1b), and fatal overdoses among patients at Northwestern connect data from that institution with Illinois State Vital records (Illinois Department of Public Health (IDPH); See Appendix 1, Figure 1c). A pilot study was originally approved for the data exchange in Figure 1c and the secure data sharing exercise was successful.

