The goal of the project is to dampen the intensity and frequency of opioid prescribing and to increase awareness and use of medication assisted therapy for persons with opioid use disorder through a cluster randomized trial. Overdose notification letters (See Appendix 2 and 3) will be sent to primary care clinicians randomized to the experimental study arm and meeting inclusion criteria at AltaMed Health Services or Northwestern Medicine. Both letters will include "if/when/then" language which advises the clinician to keep the letter's recommendations close when their next patient presents with pain. Clinicians notified of their patient's overdose will be compared to a control group receiving guideline education and no notification of their patient's overdose (Appendix 6). To quantify the effect of the notification letter, we will measure the change in clinician weekly milligram morphine equivalent (MME) prescribed to all of their patients in 6-month periods before and after receiving overdose feedback letters. The secondary outcomes include the change in proportion of patients prescribed at least 50 daily MME, buprenorphine referrals for medication assisted therapy, and access rates for referral links included in the letter.

Because the letters include patient identifying information linked to outpatient prescribing records, we requested a HIPAA waiver of authorization to match outpatient records to mortality and non-fatal overdose records. The research could not feasibly be conducted if research participants' authorization were required. AltaMed will release information under the auspices of a waiver of HIPAA authorization. USC and AltaMed have a fully executed Business Associates Agreement, Memorandum of Understanding and Data Use Agreement; Northwestern and IDPH and USC and Northwestern have a fully executed Data Use Agreement. AltaMed and Northwestern will cede to the County IRB as the IRB of record for this study.

To create the list of overdose patients for whom opioids were prescribed, outpatient records will be linked to the emergency department and, in the case of Northwestern patients, IDPH death records. Overdose data will be linked with outpatient records using matching software that complies with institutional security and privacy standards at IDPH and Los Angeles County. Where an existing direct link code is available (e.g. MRN), we will use the code.

Primary hypotheses:

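### The one coefficient named for the primary outcome (group × overdose type × time) is the difference between the fatal and nonfatal letter effects, so it does not test hypothesis 1

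*Combined protocol and SAP*

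**What the plan says.** Hypothesis 1 (section B(a), Primary hypotheses) is that clinicians in the notification group will show a "greater reduction in weekly MME from the pre- to post-period compared to clinicians randomized to the control group for fatal and non-fatal overdoses". The Study Synopsis describes the same comparison: notified clinicians "will be compared to a control group receiving guideline education and no notification" of the overdose.

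Section D then ties the primary outcome to one model quantity: "The coefficient for the group assignment, overdose type, and time interaction, also known as the difference-in-differences estimator, denotes the change over time". The change is counted in hydrocodone pills of 5 MME, and intervention prescribers are "compared to prescribers in the control group for both fatal and nonfatal overdose victims". Eq. 1 is introduced as "The regression model estimating the association between letter assignment and weekly 5 MME hydrocodone pills prescribed". It is described as a mixed-effects Poisson spline with a knot at the start of the intervention. If there are too many zero weeks, "we will use a zero-inflated or left-censored regression".

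Eq. 1 contains two-way group-by-time terms (β7 for time, β8 for time after the knot) and two three-way terms (β11 and β12). No passage names β8, β8+β12 or any other model contrast for the primary outcome. For the high-dose outcome in Eq. 2, the plan instead computes the pre-to-post change in each of the four group-by-type cells.

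The design also restricts overdose type by site. The Study Synopsis says "only non-fatal overdose letters will be sent to clinicians in Los Angeles", and section B(c) adds: "Patients with fatal overdoses in Los Angeles County will be excluded to avoid redundancy with existing notification practices".

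**The concern.** A difference-in-differences estimator for letter versus control is a two-way contrast, group by time. Adding overdose type to the interaction makes it a triple difference, which asks whether the letter effect differs between fatal and nonfatal overdoses. The sentence gives the triple difference the meaning of the two-way contrast.

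If an analyst uses the named coefficient for hypothesis 1, the trial tests effect modification by overdose type. A letter that works equally well for both types would then look like a letter that does nothing. With valid standard errors, the test would reject only at its nominal level however many clinicians are enrolled. A letter that works only after nonfatal overdoses would show a coefficient pointing away from benefit. An analyst who follows the verbal hypothesis would report a different quantity from the same fitted model.

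**Working it through.** The documents give no alpha, power, effect size or share of fatal overdoses for this coefficient, so there is no stated figure to reproduce. The check is algebra on Eq. 1, confirmed by noise-free fits.

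**Inputs from the documents**
- Coding (section D, below Eq. 1): Group is 1 for letter and 0 for control; Overdose Type is 1 for fatal and 0 for nonfatal.
- Periods (section B(e)): six months before the letter, a 30-day washout, then six months after. These are taken as 26 weeks, 30/7 = 4.29 weeks and 26 weeks.

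**Assumed for illustration only**
- Baselines of 100 (nonfatal) and 60 (fatal) pills per week, and a common trend of −0.002 per week on the log scale.
- A letter effect of −0.005 per week on the slope after the knot, unless stated otherwise.

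**Step 1. Slopes implied by Eq. 1**

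| Cell | Slope before knot | Slope change at knot |
|---|---|---|
| Nonfatal, control | β2 | β3 |
| Nonfatal, letter | β2+β7 | β3+β8 |
| Fatal, control | β2+β9 | β3+β10 |
| Fatal, letter | β2+β7+β9+β11 | β3+β8+β10+β12 |

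Letter minus control, slope change: β8 for nonfatal and β8+β12 for fatal. The fatal effect minus the nonfatal effect is β12.

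Letter minus control, pre-letter slope: β7 for nonfatal and β7+β11 for fatal. The difference is β11, which has expectation zero under randomisation whatever the letter does.

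An overall letter effect with weight w on fatal is (1−w)β8 + w(β8+β12) = β8 + wβ12. No w removes β8, so no weighting reduces this to β12. Coding the indicators −1/+1 does not help, because the three-way term stays proportional to the fatal-minus-nonfatal difference.

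**Step 2. Noise-free log-link fits of the 12 fixed terms**

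| True letter effect (nonfatal, fatal) | β8 | β12 | β11 |
|---|---|---|---|
| −0.005, −0.005 | −0.005 | 0 | 0 |
| −0.005, 0 | −0.005 | +0.005 | 0 |
| 0, −0.005 | 0 | −0.005 | 0 |
| −0.005, −0.010 | −0.005 | −0.005 | 0 |

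In the last row β12 is half the fatal effect of −0.010.

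**Step 3. Site restriction**

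Every AltaMed clinician has Overdose Type = 0. AltaMed data therefore inform β8 and never the fatal effect β8+β12, so an AltaMed benefit enters β12 only as part of what is subtracted. Suppose the letter works only at AltaMed (−0.005). If AltaMed supplies 25%, 50% or 75% of nonfatal clinician-weeks, β8 is −0.0012, −0.0024 or −0.0037, and β12 is +0.0012, +0.0024 or +0.0037. The true share is not in the documents. Section B(b) lists 134 AltaMed clinicians out of 134 + 387 = 521 (26%), but these are not enrolment counts.

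**Step 4. Dependence on scale**

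Under an additive model (checked with an uncensored linear fit of the same terms), β12 is zero for equal absolute effects (−0.3 in both types). Equal log effects of −0.005 at baselines 100 and 60 then give β12 = +0.17. Under either scale the three-way term is a difference between types.

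**Step 5. Slope change versus pre-to-post change**

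Hypothesis 1 speaks of a pre-to-post change. With time measured from the letter date, the mean pre time is −13 weeks and the mean post time is 4.29 + 13 = 17.3 weeks, which are 30.3 weeks apart. The contrast in average log rate is then:
- nonfatal: 30.3·β7 + 17.3·β8
- fatal: 30.3·(β7+β11) + 17.3·(β8+β12)

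Numbering whole weeks −26 to −1 and 5 to 30 gives 31.0 and 17.5 instead.

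With β7 = 0, β8 = −0.005 and a flat control, the log contrast is 17.3 × (−0.005) = −0.086, a rate ratio of 0.917 at any baseline. The change in predicted mean is −8.2 pills per week at baseline 100 and −4.9 at baseline 60. The scale has to be stated.

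**The case against.** The strongest reply is that the intent is clear. The synopsis, hypothesis 1 and the sentence itself describe a letter-versus-control comparison. No single coefficient could cover both overdose types, so the sentence may be a loose reference to type-specific estimates from the interaction model. Section A also asks whether nonfatal feedback has an impact similar to fatal feedback, which explains why the three-way terms are in the model. On this view the matter is one of wording.

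Part of this stands. The intent is recoverable, β12 is a legitimate secondary quantity, and Eq. 1 can supply the contrasts needed. That does not make the sentence usable. It names one coefficient, that coefficient contradicts the stated meaning, and the plan gives no rule for combining types and no weights. The choice among β8, β8+β12, an average or a pre-to-post contrast is left open until the data are seen.

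Other reservations are fair but do not bear on the main point:
- The mislabelling does not depend on the AltaMed restriction, and the AltaMed figures rest on assumed shares.
- The window weights depend on the week-numbering convention and on centring time at the letter date.
- The zero-inflated option is not worked through here. A three-way term in either part of such a model is still a between-type difference, but an effect on the overall mean would need both parts.
- For Eq. 2 the plan states no explicit letter-versus-control test. It does plan the four cell changes, from which the letter effects follow by subtraction, and it attaches no wrong coefficient to them.

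**Conclusion.** The concern holds and must be fixed. The only model quantity named for the primary outcome is a fatal-minus-nonfatal difference (β12), or a pre-letter slope difference if β11 is meant. Neither is the letter-versus-control effect in hypothesis 1. On the log scale, equal benefit for both types gives an expected coefficient of zero, benefit confined to nonfatal overdoses reverses its sign, and doubling the benefit for fatal overdoses shows only half the fatal effect. Under an additive model the zero result applies to equal absolute effects instead.

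The conclusion rests on the coding given below Eq. 1 and on algebra, not on the illustrative effect sizes, baselines or AltaMed shares. No statement about power is made, because the documents give no inputs for one.

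**What to change.** Replace the sentence in section D.

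1. State that hypothesis 1 is tested by a letter-versus-control contrast from Eq. 1. Use either the two type-specific effects (β8 for nonfatal, β8+β12 for fatal), with a rule for whether one or both must be significant, or a single average over type (β8 + wβ12) with w fixed in advance.
2. State whether the target is the slope change at the knot or a pre-to-post change. For a pre-to-post change, include the pre-letter slope terms (β7, and β7+β11 for fatal). State the scale: a difference in average log rates, or a difference in model-predicted mean pills or MME. Define how study time and the washout weeks enter, and how the contrast is formed if the zero-inflated or left-censored model is used.
3. Label β12 (with β11) as a test of effect modification by overdose type only.

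Eq. 2 can stay as it is, since its letter effects follow from the planned four-cell changes.

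The cost is SAP wording and one contrast statement. No new data are needed and neither equation changes.
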